9.3.2 Outcome

9.3.2.1 Primary outcomes

The following outcomes will be assessed, noting that outcome-specific analytic considerations such as the etiologically relevant exposure window and specific additional population restrictions (e.g., exclusion of women with teratogenic medication exposure or teratogenic infections for assessment of major congenital malformations) will be defined in the SAP.

- Pregnancy complications are:
 - Hypertensive disorders of pregnancy (preeclampsia, eclampsia, gestational hypertension)
 - Gestational diabetes
 - Bleeding during pregnancy
 - Postpartum haemorrhage
 - Pregnancy-related death

- Adverse pregnancy outcomes are:
 - Fetal death (spontaneous abortion or stillbirth)
 - Termination of pregnancy for fetal anomaly (TOPFA)
 - Any elective pregnancy termination
 - Ectopic pregnancy

- Adverse neonatal outcomes are:
 - Fetal growth restriction/small for gestational age (SGA), using sex- and gestational-age specific cutoffs¹³
 - Preterm birth (<37 full gestational weeks)
 - Low birth weight (<2500 g)
 - Major congenital malformations¹⁴
 - Microcephaly (based on head circumference)
 - Low 5-minute Apgar score
 - Neonatal death (death within 28 days of birth)

Where a signal is detected for the outcome of major congenital malformation as a composite, organ system-specific analyses will be conducted. Organ-specific major congenital malformations, according to the EUROCAT¹⁴ classification are:

- Nervous system
- Eye
- Ear, face and neck
- Congenital heart defects
- Respiratory

- Oro-facial clefts
- Digestive system
- Abdominal wall defects
- Urinary
- Genital
- Limb
- Other

9.3.2.2 Secondary outcomes

- Characteristics of Spikevax utilization according to predefined exposure categories:
 - Number and prevalence of exposed pregnancies/births any time during pregnancy/gestation;
 - Number and prevalence of pregnancies/births with one dose/two doses/more than two doses;
 - Number and prevalence of exposed pregnancies/births in each of the trimesters; trimester of first dose;
 - Maternal and newborn characteristics according to the exposure to Spikevax.

9.3.3 Covariates

The key covariates will include country of residence, calendar year of delivery, pregnant woman's age, smoking, alcohol use (whenever measured), marital status or other available socioeconomic measures, gravidity, parity, placenta previa, caesarean delivery, multifetal pregnancies, prior reproductive history (prior still birth, prior child SGA, prior pregnancy with preeclampsia) selected chronic comorbidities (cardiovascular diseases, respiratory diseases, type 2 and gestational diabetes, cancer, mental-health disorders, and autoimmune diseases [rheumatic diseases, systemic lupus erythematosus, inflammatory bowel disease, multiple sclerosis, type 1 diabetes, thyroid disorders, medication use]), selected medication use, body mass index (BMI), and history of COVID-19 infection

Specific covariates' availability may vary by database and will be described in the SAP.

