9.3. Variables

9.3.1 Exposure

The exposure will be defined by a record of receipt of at least one dose of Spikevax during pregnancy.

For the purposes of timing of exposure, trimesters of pregnancy will be defined as follows:

- First trimester: from the first day of the last menstrual period (LMP) to LMP+97 days (both dates inclusive);
- Second trimester: from LMP+98 days to earliest of (LMP+202 days, pregnancy end) (both dates inclusive);
- Third trimester: from LMP+203 days (inclusive) until pregnancy end date (not included)

Pregnancies unexposed to Spikevax vaccine will be categorized as unexposed or as exposed to other COVID-19 vaccines and other non-COVID-19 vaccines (influenza, meningococcal disease, pneumococcal disease, rubella, shingles, tuberculosis), overall and trimester-wise. Pregnancies among women who received Spikevax before LMP will be enumerated and may be used as an additional comparator, group size permitting.

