9.7.3 Methods to control/assess confounding

Crude and adjusted measures of association will be computed comparing the exposed vs the unexposed (prevalence ratios, risk ratios, mortality rate ratios). Adjustment will be performed by the covariates measured, with LMP as the anchor date. Covariates will be included in the

appropriate regression model: log-binomial regression for prevalences and risks and Cox proportional-hazards regression for incidence rate ratios. Candidate covariates for inclusion in the analyses will vary by database. A propensity-score based adjustment may be considered and will be described in a separate Statistical Analysis Plan. Table 5 shows country-specific availability of the covariates.

Table 5 Proposed candidate covariates and data availability in participating databases

Variable/data type	AVAILABILITY OF DATA IN THE DATABASE (either via diagnosis code or procedure or treatment proxy)				
	DENMARK (NATIONAL REGISTRIES)	ITALY/ARS TOSCANA	NORWAY (NATIONAL REGISTRIES)	SPAIN/SIDIAP	UK/CPRD
Pregnancy feasibility counts for interim reports	Hospital-based ICD-10 codes for pregnancy related diagnoses or codes for prenatal visits from the Insurance registry for primary care prenatal visits	Hospital-based ICD-10 codes for pregnancy related diagnoses or codes for prenatal visits from the Insurance registry for primary care prenatal visits	All pregnancies in Norway that last at least 12 weeks are captured in the Medical Birth Registry of Norway (mandatory notification to the registry, 100% coverage)	Most pregnancies will be identifiable in primary care; some might be missed without linkage to hospital data	Pregnancy information will be available in the main primary care dataset following primary care and/or secondary care contact with the patient. This will be based on Read and/or SNOMED codes.
Country of residence	YES	YES	YES	YES	YES
Calendar year of delivery	YES	YES	YES	YES	YES
Pregnant woman's age	YES	YES	YES	YES	YES
Marital or cohabiting status	YES	To be verified	YES	To be verified	YES
Smoking	YES	To be verified	YES	YES	YES
Alcohol use (also ICD codes)	YES, IF BASED ON ICD CODES	YES	YES, IF BASED ON ICD CODES	To be verified	YES

Confidential

Post-marketing safety study for COVID-19 mRNA-1273 vaccine

Protocol mRNA-1273-P905, Date: 27 September 2021, Version 1.2

Marital status or other available socioeconomic measures	YES	YES	YES	YES Other available socioeconomic measures	YES
Gravidity	YES	YES	YES	YES	YES
Parity	YES	YES	YES	YES	YES

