Placenta previa	YES	YES	YES	YES	YES
Caesarean delivery	YES	YES	YES	YES	YES
Multifetal pregnancy	YES	YES	YES	YES	YES
Prior (before participating pregnancy) still birth	YES	YES	YES	To be verified	YES
Prior (before participating pregnancy) child SGA	YES	YES	YES	YES	YES
Prior (before participating pregnancy) pregnancy with preeclampsia	YES	YES	YES	To be verified	YES
Cardiovascular diseases (eg hypertension, migraine)	YES	YES	YES	YES	YES
Respiratory diseases (eg asthma COPD)	YES	YES	YES	YES	YES
Type 2 diabetes	YES	YES	YES	YES	YES
Gestational diabetes	YES	YES	YES	YES	YES
Cancer	YES	YES	YES	YES	YES
Mental-health disorders	YES	YES	YES	YES	YES
Rheumatic diseases	YES	YES	YES	YES	YES
Systemic lupus erythematosus	YES	YES	YES	YES	YES
Inflammatory bowel disease	YES	YES	YES	YES	YES
Multiple sclerosis	YES	YES	YES	YES	YES
Type 1 diabetes	YES	YES	YES	YES	YES

Outpatient prescriptions/dispensings	YES	YES	YES	YES	NO
BMI or obesity	YES	YES	YES	YES	YES
History of COVID-19 infection	YES	YES	YES	YES	YES
HCRU measures (mother)	YES	YES	YES	YES	YES

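### Caesarean delivery, placenta previa and gestational diabetes are listed as covariates without restriction to before pregnancy, which contradicts the LMP anchor and leaves the main models open to adjustment for consequences of vaccination

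*Protocol*

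**What the plan says.** Section 9.3.3 lists the key covariates, including "gravidity, parity, placenta previa, caesarean delivery, multifetal pregnancies, prior reproductive history". The last of these items has its own stated content: earlier stillbirth, earlier SGA child and earlier preeclampsia. Caesarean delivery and placenta previa stand outside it. Further on, under chronic comorbidities, the list has "type 2 and gestational diabetes, cancer, mental-health disorders".

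Table 5, in section 9.7.3, repeats all three as candidate covariates. It labels some rows explicitly as history, for example "Prior (before participating pregnancy) pregnancy with preeclampsia", and does the same for stillbirth and SGA child. The rows for caesarean delivery, placenta previa and gestational diabetes carry no such label.

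On timing, section 9.7.3 states: "Adjustment will be performed by the covariates measured, with LMP as the anchor date". The abstract describes the covariates as maternal characteristics from before pregnancy. Section 9.3.1 defines exposure: "The exposure will be defined by a record of receipt of at least one dose of Spikevax during pregnancy". Section 9.3.2.1 lists "Gestational diabetes" among the primary outcomes.

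The adjusted estimates come from "log-binomial regression for prevalences and risks and Cox proportional-hazards regression for incidence rate ratios", with a propensity score as an option. On the standing of the list, section 9.7.3 says: "Candidate covariates for inclusion in the analyses will vary by database".

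**The concern.** The objective is the total effect of vaccination in pregnancy on each outcome. A variable determined after the dose, and possibly by it, does not belong in the main model for that effect. If vaccination raised the frequency of a complication that leads to caesarean, and caesarean raised the risk of postpartum haemorrhage or a low Apgar score, a model containing caesarean would hide that route. If the covariate and the outcome share an unmeasured cause, conditioning on the covariate can also create an association where none exists.

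Gestational diabetes raises a further problem. It is on the covariate list and on the outcome list, and no rule in the protocol takes it out of the model in which it is the outcome.

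One common program goes to all data access providers (section 9.6), and section 12 says only one data extraction is feasible. A misread list would therefore be repeated in all five databases and in any pooled estimate.

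**Working it through.** The plan gives no figure on this point, so the first check is of the text.

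**Step 1. Can the three items be known at the anchor date?**

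| Item | Where listed | Marked as history? | If it means the index pregnancy |
|---|---|---|---|
| Caesarean delivery | 9.3.3, Table 5 | No | Occurs at delivery, so always after a dose in pregnancy |
| Placenta previa | 9.3.3, Table 5 | No | After LMP; before or after the dose |
| Gestational diabetes | 9.3.3 (comorbidities), Table 5 | No | After LMP; before or after the dose; also a primary outcome |
| Stillbirth, SGA child, preeclampsia | 9.3.3, Table 5 | Yes | Not applicable |

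None of the three, as an index-pregnancy event, can be known at LMP. Either they mean history and the label is missing, or they mean the index pregnancy and the anchor is broken.

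**Step 2. Does the anchor settle it?** Not by itself. The same list holds calendar year of delivery and multifetal pregnancy, and neither is fixed at LMP. A programmer cannot infer that every listed item is to be read as of LMP.

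**Step 3. What would mediator adjustment remove?** All inputs here are assumed; the protocol supplies none. Let p be the prevalence of the covariate in the unexposed, a the ratio by which vaccination raises it, b the ratio by which it raises the outcome, and d the direct prevalence ratio (PR).

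Total PR = d × [1 + p·a·(b − 1)] / [1 + p·(b − 1)]. A model that fully adjusts for the covariate returns only d.

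With d = 1, p from 5% to 20%, a from 1.2 to 2.0 and b from 1.5 to 3.0:

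- Smallest: (1 + 0.05 × 1.2 × 0.5) / (1 + 0.05 × 0.5) = 1.030 / 1.025 = 1.005
- Middle: (1 + 0.10 × 1.5 × 1.0) / (1 + 0.10 × 1.0) = 1.15 / 1.10 = 1.045
- Largest: (1 + 0.20 × 2.0 × 2.0) / (1 + 0.20 × 2.0) = 1.80 / 1.40 = 1.29

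The adjusted estimate is 1.00 in each case. With d = 1.2, the total PR runs from 1.21 to 1.54, against 1.20 after adjustment. If a = 1, nothing is lost.

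A concrete case, also assumed: vaccination raises caesarean from 20% to 25%, and haemorrhage is 12% with caesarean and 4% without. The total ratio is (0.25 × 0.12 + 0.75 × 0.04) / (0.20 × 0.12 + 0.80 × 0.04) = 0.060 / 0.056 = 1.07. Within caesarean strata it is 1.00.

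**Step 4. Collider bias.** Assume an unmeasured cause present in 20%, and baseline risks of 5% for both covariate and outcome. The cause multiplies each by 2 or 3, vaccination multiplies the covariate by 1.5 or 2, and neither vaccination nor the covariate affects the outcome. The true PR is 1. Among pregnancies without the covariate, the largest setting (3 and 2) gives:

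- Unexposed: (0.2 × 0.85 × 0.15 + 0.8 × 0.95 × 0.05) / (0.17 + 0.76) = 0.0635 / 0.93 = 0.0683
- Exposed: (0.2 × 0.70 × 0.15 + 0.8 × 0.90 × 0.05) / (0.14 + 0.72) = 0.0570 / 0.86 = 0.0663
- Ratio: 0.97

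The other three settings give 0.986 to 0.996, and the stratum with the covariate gives 1.00 throughout. Exchanging the exposed and unexposed groups (a vaccine that lowers the covariate) inverts the ratio to 1/0.9707 = 1.03. The direction therefore depends on the signs of the paths.

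**The case against.** The strongest reply is that the protocol already has a timing rule. With covariates anchored at LMP and described in the abstract as pre-pregnancy characteristics, the three could enter only as history. The list is also headed as candidates, and choosing covariates per outcome, including dropping gestational diabetes from its own model, is ordinary content for the statistical analysis plan. Several genuine pre-pregnancy items in Table 5, such as parity and type 1 diabetes, carry no history label either, and gestational diabetes under chronic comorbidities may well mean a past diagnosis.

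Much of this stands. A reader might infer that the sponsor has settled on adjusting for mediators; the documents do not show that. They show a list and an anchor that contradict each other. Nor do all three items necessarily follow vaccination: previa or gestational diabetes diagnosed before a later dose could be a confounder, and section 9.9 itself warns that morbidity may drive vaccination. Only an index caesarean must follow the dose.

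What does not stand is that the anchor repairs the list. It visibly does not govern every item, caesarean and previa sit beside multifetal pregnancy and outside the history item, and section 9.3.3 defers only covariate availability to the analysis plan. No rule anywhere excludes post-exposure variables.

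A reader might also set the illustrative 1.07 beside the 1.07 in Table 3 and conclude that adjustment would hide an excess the study could otherwise exclude. That comparison fails. The Table 3 value belongs to an outcome at 10% prevalence, whereas the illustration has 5.6%. The 5% rows give 1.11 at best.

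**Conclusion.** The point holds as a contradiction within the protocol that should be resolved before programming. Followed as written, the list would put an index-pregnancy caesarean into models for outcomes such as postpartum haemorrhage and low Apgar score, where it would bias a total-effect estimate. It would also allow gestational diabetes to be adjusted for in its own analysis.

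The size cannot be derived from the documents. On the assumed inputs, the part removed lies between 0.5% and 29% on the ratio scale. This rests on a single binary covariate, no interaction, and a vaccine effect on that covariate. It would be wrong to read this as removing part of every real effect: only the part passing through these variables is lost, and none if vaccination does not affect them. Nor is the net error necessarily toward no effect, since collider bias can go either way.

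**What to change.** In section 9.3.3 and Table 5:

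- Remove index-pregnancy caesarean delivery from every main adjustment or propensity model.
- Admit placenta previa and gestational diabetes to the main model only as history recorded before LMP, where the database has it, and label the rows accordingly.
- Never adjust for index-pregnancy gestational diabetes where it is the outcome.
- Use index-pregnancy events only descriptively or in a labelled sensitivity analysis, for example one restricted to diagnoses made before the dose in late-exposure analyses.
- State that history of COVID-19 infection is taken up to LMP, or up to the dose in a time-dependent analysis.

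The edit is to one list and one table. It has two costs. Some control is lost for previa or gestational diabetes diagnosed before a later dose; the sensitivity analysis addresses this in part. And the history items may not be available everywhere: Table 5 has no rows for previous caesarean, previa or gestational diabetes, and two of Spain's three listed prior-event items are still to be verified.

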The maternal and pregnancy outcomes will be addressed using the prevalence study design; neonatal outcomes and pregnancy related death in the cohort design. In the routinely collected data, pregnancies are typically identifiable on the date of pregnancy end, either in a birth or in an abortive outcome. All identifiable pregnancies will be included, and their start and end dates will be determined based on the LMP or gestational age at end, depending on data availability. Outcomes examined in this design include gestational diabetes, hypertensive disorders of pregnancy, pregnancy-related death, fetal growth restriction/small for gestational age, spontaneous abortion, stillbirth, preterm birth, major congenital malformations, microcephaly, neonatal death, and termination of pregnancy for foetal anomaly (TOPFA).

Population

This study will be multi-database, utilizing routinely collected health data of various types in five European countries: Denmark, Italy, Norway, Spain, and the United Kingdom. Pregnancies ending between 6 January 2021 (date of the earliest approval of the COVID-19 Moderna Vaccine in Europe) and 31 December 2022 will be identified and classified according to the exposure to the COVID-19 Moderna Vaccine, overall and according to the trimester of exposure. The study period may be extended if the size of the study population is insufficient to study specific outcomes of interest.

The study population will encompass all pregnancies, identifiable in the databases, ending in a live or still birth, a spontaneous abortion, or an induced abortion, as identifiable in the participating databases. In Denmark and Norway, all pregnancies ending in a live or still birth, as well as pregnancies leading to a hospital encounter due to termination will be identifiable.

Variables

Members of the analysis populations (pregnancies, births, depending on the outcome) will be described with respect to available demographic characteristics, medical history, medication use, receipt of other vaccines, and characteristics of the exposed pregnancy. Pregnancies and births will be classified according to the exposure status Spikevax, overall and by trimester.

The outcomes of interest will include pregnancy complications, adverse pregnancy outcomes, and adverse neonatal outcomes.

Covariates will include maternal pre-pregnancy demographic and clinical characteristics, such as age, smoking, body mass index, chronic morbidities and medication use.

Data sources

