9.9 Limitations of the research methods

An important limitation of the research method is that currently Spikevax is not indicated for use in pregnancy according to the current label, implying that at least at the initial study stages, the number of exposed pregnancies may be low, potentially affecting precision of the resulting estimates of association. Furthermore, owing to typical data flow in routinely collected data, only completed pregnancies (ending in a birth or an abortive outcome) are identifiable. Ongoing pregnancies cannot be identified. A further limitation is heterogeneity of the different data sources in their ability to identify all pregnancy outcomes of interest. Finally, unmeasured confounding due to non-comparability of vaccinated and non-vaccinated pregnancies (healthy or sick vaccinee), at least at the start of the vaccination of pregnant women, cannot be ruled out. If pregnant women with chronic diseases or those taking medication are more likely to be vaccinated, uncontrolled confounding by morbidity will produce an upward bias in the association between vaccination and some AESI, whenever these chronic diseases are themselves associated with adverse outcomes.

A potential misclassification of exposure timing (eg. if LMP is imprecise) may produce a downward bias, if an association exists.

Because, by definition, pregnancy and neonatal outcomes are prevalent outcomes, one cannot enumerate the cohort of conceptuses initiating the follow-up. Early pregnancies that end in a spontaneous abortion and do not lead to a health care record are not detectable in the available data sources. At the same time, shorter pregnancies may be overestimated in the study population because of being identified by pregnancy end.²¹

Finally, for the outcome major congenital malformations, the standard (EUROCAT)¹⁴ definitions recommend follow-up until age 1 year, which will not be available for all neonates in currently defined study populations. This under ascertainment will lower the sensitivity of the outcome, which, if not related to vaccination status, should not bias associations

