The Italian National Healthcare System is organized at regional level: the national government sets standards of assistance and a tax-based funding for each region, and regional governments are responsible to provide to all their inhabitants. Tuscany is an Italian region, with around 3.6 million inhabitants. The Agenzia Regionale di Sanita' della Toscana (ARS) is a research institute of the Tuscany Region. The ARS database comprises all information that are collected by the Tuscany Region to account for the healthcare delivered to its inhabitants. Moreover, ARS collects data from regional initiatives. All the data in the ARS data source can be linked with each other at the individual level, through a pseudo-anonymous identifier. The ARS database routinely collects primary care and secondary care prescriptions of drugs for outpatient use, and is able to link them at the individual level with hospital admissions, admissions to emergency care, records of exemptions from copayment, diagnostic tests and procedures,

causes of death, mental health services registry, birth registry, spontaneous abortion registry, induced terminations registry. A pathology registry is available, mostly recorded in free text, but with morphology and topographic SNOMED codes. Mother-child linkage is possible through the birth registry. Vaccine data is available since 2016 for children and since 2019 for adults. The ARS database was characterized in the ADVANCE project and considered fit for purpose for vaccine coverage, benefits and risk assessment when using the new vaccine registry (from 2019).

Norway: Norwegian population registries

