The Information System for Research in Primary Care (Sistema d'Informació per al Desenvolupament de la Investigació en Atenció Primària' - SIDIAP; www.sidiap.org) was created in 2010 by the Catalan Health Institute (CHI) and the IDIAPJGol Institute. It includes information collected since 01 January 2006 during routine visits at 278 primary care centers pertaining to the CHI in Catalonia (North-East Spain) with 3,414 participating GPs. SIDIAP has pseudo-anonymized records for 5.7 million people (80% of the Catalan population) being highly representative of the Catalan population. The SIDIAP data comprises the clinical and referral events registered by primary care health professionals (GPs, pediatricians and nurses) and administrative staff in electronic medical records, comprehensive demographic information, community pharmacy invoicing data, specialist referrals and primary care laboratory test results. It can also be linked to other data sources, such as the hospital discharge database, on a project by project basis. Health professionals gather this information using ICD-10 codes, ATC codes and structured forms designed for the collection of variables relevant for primary care clinical management, such as country of origin, sex, age, height, weight, body mass index, tobacco and alcohol use, blood pressure measurements, blood and urine test results. In

relation to vaccines, SIDIAP includes all routine childhood and adult immunizations, including the antigen and the number of administered doses. Encoding personal and clinic identifiers ensures the confidentiality of the information in the SIDIAP database. The SIDIAP database is updated annually at each start of the year. With the COVID-19 pandemic, there is the possibility to have shorter term updates in order to monitor the evolution of the pandemic. Recent reports have shown the SIDIAP data to be useful for epidemiological research. SIDIAP is listed under the ENCePP resources database www.encepp.eu/encepp/resourcesDatabase.jsp. The SIDIAP database was characterized in the ADVANCE project and considered fit for purpose for vaccine coverage, benefits and risk assessment.

United Kingdom: CPRD & HES

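### Vaccination history before LMP is missing from the adjustment covariates, although the protocol concedes healthy-or-sick-vaccinee non-comparability and most of its sources hold vaccine records

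*Protocol*

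**What the plan says.** The protocol refers to other vaccines in three places.

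- The Variables part of the abstract says that the analysis populations will be described by "available demographic characteristics, medical history, medication use, receipt of other vaccines, and characteristics of the exposed pregnancy".
- Section 9.3.1 sorts Spikevax-unexposed pregnancies by receipt of other COVID-19 vaccines and of named non-COVID-19 vaccines, influenza among them, overall and by trimester.
- Section 9.7.5 allows, without committing to it, comparators made up of pregnancies with other contemporaneous vaccinations such as influenza, or of pregnancies vaccinated before LMP.

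The adjustment set is separate. The abstract illustrates the covariates with items "such as age, smoking, body mass index, chronic morbidities and medication use". Section 9.3.3 gives the fuller list, which closes with "selected medication use, body mass index (BMI), and history of COVID-19 infection". Table 5 in section 9.7.3 sets out candidates country by country. Vaccination history appears in none of these. Section 9.7.3 measures covariates with LMP as the anchor date. Section 9.3.3 adds that "Specific covariates' availability may vary by database and will be described in the SAP".

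Section 9.9 says that it cannot rule out "unmeasured confounding due to non-comparability of vaccinated and non-vaccinated pregnancies (healthy or sick vaccinee". The only direction it spells out is upward, from morbidity.

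On data, the Italian entry in Annex 3 states "Vaccine data is available since 2016 for children and since 2019 for adults" and the Spanish entry states "SIDIAP includes all routine childhood and adult immunizations". The Danish entry mentions vaccines dispensed and vaccinations in primary care, and the UK entry mentions immunisations. The Norwegian entry does not mention non-COVID-19 vaccine data.

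**The concern.** A woman's earlier uptake of vaccines is a direct recorded marker of her willingness to be vaccinated. Such willingness may go with other behaviour that affects preterm birth, growth restriction and other primary outcomes. Most listed covariates are demographic, obstetric or morbidity items, which bear mainly on the sick vaccinee. Smoking, alcohol, BMI, socioeconomic measures and maternal health-care use touch the healthy vaccinee less directly. If vaccine-seeking behaviour is associated with lower outcome risk and is not adjusted for, the ratios are pulled down, and in a safety study that can mask harm. Section 9.9 treats this non-comparability as unmeasured, yet four of the five sources are described as holding records that would measure part of it.

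**Working it through.** **1. What is in the list.** Leaving out the feasibility-count row, Table 5 has 30 covariate rows. None concerns vaccination. The nearest are outpatient prescriptions/dispensings (in Denmark the prescription registry also covers dispensed vaccines) and maternal health-care use, marked as available in all five sources.

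**2. The protocol's own precision, for scale.** Table 3 gives upper limits under a true prevalence ratio of 1, with no allowance for confounding. For small for gestational age (SGA) with 16,667 exposed, 1:5 allocation and prevalence 0.1:

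- SE = sqrt[0.9/(16,667 × 0.1) + 0.9/(83,335 × 0.1)] = sqrt(0.000540 + 0.000108) = 0.0255
- 80% probability: exp[(1.960 + 0.842) × 0.0255] = 1.074 (Table 3: 1.07)
- 90% probability: exp[(1.960 + 1.282) × 0.0255] = 1.086 (Table 3: 1.09)

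All 24 rows of Table 3 reproduce to within 0.01.

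**3. Size of the confounding, under assumptions.** The protocol gives no uptake figures and no outcome association, so every input here is assumed. For a binary marker with prevalence p1 in the exposed and p0 in the unexposed, and outcome ratio RR, the null prevalence ratio is multiplied by

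B = [1 + p1(RR − 1)] / [1 + p0(RR − 1)].

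With p0 = 0.20:

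| p1 | RR 0.9 | RR 0.8 | RR 0.7 |
|---|---|---|---|
| 0.30 | 0.97/0.98 = 0.990 | 0.94/0.96 = 0.979 | 0.91/0.94 = 0.968 |
| 0.40 | 0.96/0.98 = 0.980 | 0.92/0.96 = 0.958 | 0.88/0.94 = 0.936 |
| 0.50 | 0.95/0.98 = 0.969 | 0.90/0.96 = 0.938 | 0.85/0.94 = 0.904 |

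In the middle case a true ratio of 1.10 would read 1.10 × 0.958 = 1.05. The 80% limit for SGA would move from 1.074 to about 1.074 × 0.958 = 1.03. That 4% shift is over half of the 0.07 margin that Table 3 claims for this row.

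**4. The opposite direction.** If earlier vaccination marks sicker women, RR exceeds 1. With p0 = 0.20, RR = 1.11 and p1 = 0.30 give 1.033/1.022 = 1.01. RR = 1.25 and p1 = 0.50 give 1.125/1.05 = 1.07.

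**5. How much adjustment would recover.** The factors in steps 3 and 4 apply before adjustment for correlated covariates, so they are upper bounds on the gain. In simulated data where influenza history is only a proxy for an unmeasured trait, and morbidity and health-care use are already adjusted for, adding it moved a null ratio from 0.893 to 0.902 in one setting and from 0.904 to 0.928 in another. The shares of the remaining bias removed are 0.009/0.107 = 8% and 0.024/0.096 = 25%. Other assumed parameters gave about 3 to 13%. These runs build in the healthy-vaccinee direction and illustrate only that the gain is partial.

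**6. Look-back.** A term pregnancy (taken as 40 weeks) ending on 6 January 2021, the start of the study period, has its LMP around 1 April 2020. A history covering two earlier influenza seasons would reach into 2018/19, which began before Italian adult vaccine records start in 2019. Section 9.7.7 says that absence of a record is usually read as absence of a condition, and it plans no imputation. A count over two seasons would therefore be under-recorded for the earliest Italian pregnancies. These are disproportionately unexposed because rollout had only begun, so the error would be related to exposure.

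**The case against.** The strongest reply is that nothing is finally excluded. Section 9.3.3 is worded inclusively, Table 5 holds proposed candidates, and database availability and any propensity score are left to the SAP, so the SAP could add the variable. This stands as far as it goes: the omission is not shown to be permanent. But the protocol sets out the candidate list row by row and country by country, and what it defers is availability and the optional propensity score. Naming the covariate before data are seen is reasonable.

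A reader might infer that information on other vaccines goes unused altogether. It does not: it defines comparator categories in section 9.3.1 and an optional comparator in section 9.7.5. Section 9.7.5 also plans a negative-control exposure analysis for malformations. The gap is confined to adjustment.

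A reader might also infer that the needed variable is already collected. The abstract gives no time window, and section 9.3.1 classifies by trimester. History before LMP is a different variable. Annex 3 suggests that the records exist in four sources, but the protocol does not say that this history will be extracted.

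Finally, a reader might infer that Spikevax will look safer than it is. Section 9.9 names healthy and sick vaccinees and spells out only upward bias, and step 4 of the working shows that the factor can reverse.

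**Conclusion.** The point holds as a specific gap in the adjustment set: vaccination history before LMP is absent from section 9.3.3 and Table 5, while section 9.9 concedes the non-comparability that it would partly capture. Some avoidable confounding by vaccine-seeking behaviour may therefore remain in the exposed-versus-unexposed ratios. Bias towards apparent safety is possible but not established.

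The factor of about 0.90 to 0.99 rests wholly on assumed uptake (20% in the unexposed, 30 to 50% in the exposed) and assumed outcome ratios (0.7 to 0.9), before other adjustment. Nothing in the protocol supports applying those ratios to every outcome, malformations in particular. If earlier vaccination marks sicker women, the factor exceeds 1. The shift could be of the same order as the best precision in Table 3, but its size cannot be fixed from the document, and the covariate would remove only part of it. This is a worthwhile, inexpensive improvement and does not by itself invalidate the planned comparisons.

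**What to change.** Add one candidate covariate to section 9.3.3 and one row to Table 5: receipt of non-COVID-19 vaccines (for example influenza) before LMP, yes/no. Specify that:

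- availability is stated by database, with Norway marked as to be verified, as other rows already do;
- the look-back window is one that is fully observed for every pregnancy in that source, which in Italy means respecting the 2019 start of adult vaccine records. A yes/no item over such a window avoids the problem of a two-season count;
- vaccines received during the index pregnancy are excluded, in keeping with the LMP anchor in section 9.7.3;
- the covariate enters the adjusted models wherever it is available.

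The cost is one table row and one derived variable per source, plus confirmation that the earlier vaccine records are within each extraction. No pregnancies are lost. The small downside is that the variable is a partial proxy and may not exist everywhere. Norway accounts for 60,000 of the 200,000 annual births in Table 2 (60,000 + 25,000 + 60,000 + 45,000 + 10,000), so up to 30% of births might be analysed without it.
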